11.1.4. Severity AEs

The different categories of intensity (severity) are characterized as follows:

- Mild:* The event is transient and easily tolerated by the patient.
- Moderate:* The event causes the subject discomfort and interrupts the patient's usual activities.
- Severe:* The event causes considerable interference with the patient's usual activities.

11.1.5. Causality of AEs

The relationship of each AE to study medication will be assessed using the following categories:

Related: An AE that follows a reasonable temporal sequence from administration of a drug (including the course after withdrawal of the drug), or for which possible involvement of the drug cannot be ruled out, although factors other than the drug, such as underlying diseases, complications, concomitant drugs and concurrent treatments, may also be responsible.

Not Related: An AE that does not follow a reasonable temporal sequence from administration of a drug and/or that can reasonably be explained by other factors, such as underlying diseases, complications, concomitant drugs and concurrent treatments.

11.1.6. Start and Stop Dates

The start date of the AE is the date that the first signs/symptoms were noted by the patient and/or physician.

The stop date of the AE is the date at which the patient recovered, the event resolved but with sequela or the patient died. If AE is ongoing at the moment of end of observation, it should be indicated in the CRF.

11.1.7. Frequency

AEs (eg, vomiting) or those which occur repeatedly over a period of consecutive days are intermittent. All other events are *continuous*.

11.1.8. Action Concerning Study Medication

- *Drug withdrawn* – a study medication is stopped due to the particular AE.
- *Dose reduced* - the dose was reduced due to the particular AE.
- *Dose Increased* – the dose was increased due to the particular AE
- *Dose not changed* – the particular AE did not require stopping a study medication.
- *Dose Interrupted* – the dose was interrupted due to the particular AE
- *Unknown* – only to be used if it has not been possible to determine what action has been taken.

11.1.9. Outcomes of AEs

- *Fatal*: The patient died due to the AE. If the patient died due to other circumstances than the AE the outcome should be stated as ‘Not recovered’ or ‘Recovering’. The date of death will be recorded.

- *Recovered/Resolved*: The patient has fully recovered from the event or the condition has returned to the level observed at baseline

- *Recovering/Resolving*: The event is improving but the patient is still not fully recovered

- *Not Recovered/Not Resolved*: The event is ongoing at the time of reporting and the patient has still not recovered

- *Recovered with Sequelae/Resolved with Sequelae*: As a result of the event, the patient suffered persistent and significant disability/incapacity (e.g. became blind, deaf or paralysed).

- *Unknown*: If Outcome is not known or not reported.

11.2. Reporting of Adverse Events

11.2.1. Legislation for Pharmacovigilance

Applicable legal base Pharmacovigilance for the Russian Federation is following:

- Federal law of 12 April 2010 “On the Circulation of Pharmaceuticals”

- **Good Pharmacovigilance Practice of Eurasian Economic Union” (came into force May, 06, 2017).**

- **Roszdravnadzor order #1071 “On Approval of the Pharmacovigilance Procedure” (came into force April, 01, 2017).**

- Order of the Ministry of health care and social development of 26 August 2010 N757n “On approval of the procedure for drug safety monitoring, reporting of side effects, serious adverse drug reactions, unexpected adverse drug reactions”

- RF Government statement of 30.06.2004 #323 «On approval of the Federal Service on Surveillance in Healthcare»

- RF Government statement of 15.10.2012 №1043 «On approval of the Federal State Supervision in medicine circulation»

Applicable legal base Pharmacovigilance for the Republic Kazakhstan is following:

- The Code of Republic of Kazakhstan on people's health and the health system (with amendments and additions from 19.05.2015)

- Order of the Minister of Health of the Republic of Kazakhstan dated November 19, 2009 № 744 On approval of rules of clinical trials and (or) pharmacological tests of medicines, medical devices and medical equipment (with amendments from September 28, 2012)

- Order No. 421 of the Health and Social Development Minister of the Republic of Kazakhstan as of 29 May 2015 On Approval of the Rules for Medicines Pharmacovigilance and Monitoring of Adverse Reactions of the Medicines, Medical devices and Medical Equipment

- Order #9 on amendments to the Order #735 of the Minister of Health of the Republic of Kazakhstan from 18 November, 2009 On approval of the rules for state registration, renewal and amendments into the registration dossier of the Medicines, Medical devices and Medical Equipment

11.2.2. AE Reporting Form

All AEs will be documented in the special AE page of the CRF – “AE reporting form”. The following information will be documented for each event:

- event term,
- start and stop date/ ongoing {and time},
- severity,
- Investigator’s opinion of the causal relationship between the event and administration of study medication(s) (related or not related),
- action concerning study medication,
- outcome of AE,
- seriousness.

The “AE reporting form” contents all information which is required to the form “Report about side effect, adverse drug reaction or lack of expected therapeutic endpoint of drug”.

11.2.3. Collection and reporting of AE

Any AEs observed during the study and follow-up information on these should be reported by the investigator as soon as possible after having knowledge to the Sponsor and/or responsible CRO. Start of AEs collection: AEs must be collected from start of Edarbi® treatment.

Collection of AEs will commence from the time of the first Edarbi® intake (Baseline visit). Routine collection of AEs will continue until Observational visit 4 (Final visit).

A physician must report all reportable AEs on the special “AE reporting form” provided by the Sponsor. The physician should record only one AE per 1 “AE reporting form”. The physician

has to record the diagnosis if available. If no diagnosis is available, the physician should record each sign and symptom as separate reports.

11.2.4. Collection and reporting of SAE and pregnancies

The physician should report all reportable SAEs and pregnancies to Takeda Pharmacovigilance Drug Safety Officer **immediately (within 24 hours)** after obtaining knowledge of the event by one of the following way:

- by email to **Protected Personal Data** using the separate “AE reporting form”,
- by fax number: [name] using the separate “AE reporting form”.

If information is not available at the time of the first report becomes available at a later date or upon on the sponsor’s request, the investigator should complete an additional SAE form and provide it by one of mentioned above way **immediately within 24 hours** of receipt. Copies of any relevant data from the hospital notes (eg, ECGs, laboratory tests, discharge summary, postmortem results) should be sent to the addressee, if requested.

In any case all SAEs should be followed up until resolution or permanent outcome of the event. The timelines and procedure for follow-up reports are the same as those for the initial report.

11.2.5. Safety reporting to Investigators, IRBs or IECs, and Regulatory Authorities

All safety-related data on study patient collected in the study database or reported to Takeda according to the normal procedure for marketed drugs, e.g. serious and non-serious AEs, will be summarised in the Non-Interventional Study Report.

In case of changes in benefit-risk assessment of Edarbi® the Sponsor will also prepare an expedited report for safety issues. The investigational site also will forward a copy of all expedited reports to their IRB or IEC.

Specialized safety reporting in the Russian Federation

The Sponsor is responsible for reporting all ADRs, SADR and pregnancies to the Federal Service on Surveillance in Healthcare not later than 15 calendar days from the day when relevant information becomes known to the sponsor.

Periodic Safety Update Report (PSUR) contains drug safety information obtained from spontaneous reports, literature and in clinical trials for a certain reporting period. According to the Russian legislation PSUR submission periodicity is determined by International Birth Date of a drug. PSUR submission time: Every 6 months during first 2 years from International Birth Date;

- Annually during the following 2 years;
- Once in three years – thereafter.

Specialized safety reporting in the Republic Kazakhstan:

The Investigator informs the Authorized organization, Ethics Committee and the Sponsor/responsible CRO about all ADRs not later than 15 calendar days from the day when relevant information becomes known.

Periodic Safety Update Report (PSUR) contains drug safety information obtained from spontaneous reports, literature and in clinical trials for a certain reporting period.

The marketing authorization holder, within the marketing authorization validity period, shall provide the authorized organization with the Periodic Safety Report from the date of registration in the Republic of Kazakhstan in accordance with the following standard periodicity:

- once every six months within two years after registration;
- annually - within the next three years;
- then - every three years or after receiving a report from the central office (if applicable);
- in future - upon subsequent medicine re-registration - once in five years;
- immediately at the authorized organization's request.

12 Data Quality Control and Assurance

12.1 Quality Control

12.1.1. Training of investigators

Before start of data collection all investigators will be trained on:

- the background and objectives of the study,
- study procedures,
- safety reporting,
- ethical regulations,
- data entering and database
- etc.

12.1.2. Quality reviews during the study conducting

The data quality will be assured by using the following methods of quality review:

- telephone interview,

- monitoring in the study sites (the monitoring will consist of two parts: on-site interview and verification of the compliance of the data presented in the CRF with the data of the primary documentation - source data verification (SDV)).

Due to non-interventional study design source documents will be partly reviewed for verification of data recorded on the CRF. Source documents are defined as original documents, data, and records. The investigator and institution guarantee access to source documents by the Sponsor or its designee (CRO) and by the IRB or IEC.

All aspects of the study and its documentation can be patient to review by the sponsor or responsible CRO, including but not limited to the Investigator's Binder, patient medical records, informed consent documentation and review of CRF and associated source documents. It is important that the investigator and other study personnel are available during the monitoring visits and that sufficient time is devoted to the process. The investigator and institution guarantee access to source documents by the sponsor or responsible CRO and by the IRB or IEC.

Due to the non-interventional study design it can be able to conduct quality review only on subset of investigational sites and case report forms. Exact extent of quality reviews will be defined in the Monitoring Plan. The detailed description of the quality review will be presented in the Monitoring Plan, the Data Management Plan (DMP) and Statistical Analysis Plan.

The investigational sites where telephone interview or monitoring visit will take place will be determined randomly. Due to long overall duration of the study several waves of quality reviews will be performed.

12.1.3. Data checks and data queries

The data from paper CRFs will be doubly entered into the common database by the authorized officers of CRO in accordance with the internal standard operational procedures. After completion of the entry process, computer logic checks will be run to identify items, such as inconsistent dates, missing data, and questionable values. Queries may be issued by the sponsor and responsible CRO and will be answered by investigators.

Corrections to CRF are recorded in an audit trail that captures the old information, the new information, identification of the person making the correction, the date the correction was made, and the reason for change. Reasons for significant corrections should additionally be included.

12.1.4. Quality Assurance Audits

The Quality Assurance (QA) unit or out-sourced by the Sponsor agency may audit the study to ensure that study procedures comply with the protocol and standard operating procedures, and that collected data is correct and complete.

12.2. Inspection by IRB/IEC or Competent Authority

Representatives from IRB/IEC or Competent Authority may in rare cases wish to inspect the study on site. Upon receiving notification of such inspection, the investigator must immediately contact to the Sponsor and must make the records available as requested. The Inspector must be reminded up front that consent to access to personal data has not been obtained from the participants in this study.

12.3. Data Management

12.3.1. Data Management Plan

Data Management will be carried out according to a Data Management Plan, which must be written and approved before the design of the study database is finalised. Responsible CRO will provide all the data management service including data transferring, data clarification and quality control of the process. The data management provider should approve all data formats before the data collection tools are made available to the sites.

The data from paper CRFs will be doubly entered into the common database by the authorized officers of CRO in accordance with the internal standard operational procedures. After completion of the entry process, computer logic checks will be run to identify items, such as inconsistent dates, missing data, and questionable values. Queries may be issued by the Sponsor and responsible CRO and will be answered by investigators.

12.3.2. Data privacy

The sponsor and responsible CRO affirm and uphold the principle of the patient's right to protection against invasion of privacy. The personal data of the NIS participants will be kept and processed with observance of the provisions of the RF federal law No. 152 "On personal data". Throughout this study, a patient's source data will only be linked to the study database or documentation via a unique identification number (for details, please, see Sections 8.5, 8.6., 8.7., 8.9).

If the written informed consent of a patient is known not to be available in spite of it being required, data for this patient is not entered into or is deleted from the database.

If a patient is included in the study in spite of being treated off-label (not according to the local SmPC), data is kept in the database and analysed separately and as part of the overall analyses as described in the Statistical Analysis Plan.

The patients will be identified in the database only by patient identification code (for details, please, see the section 8.7)

12.3.3. Case Report Form (CRF)

Both types of CRF – electronic and paper will be used in the study. The decision about type of CRF should be taken by investigator before start of ICF signing.

The sponsor or responsible CRO will supply investigators with paper CRFs if investigator chooses the paper type of CRF. The CRF must be completed in Russian. All data are entered directly into CRF. The investigator must sign off the complete data set for each patient, confirming the collected data. Furthermore, the investigator must retain full responsibility for the accuracy and authenticity of all data entered on the CRF. ADR data reported according to section 11 and data on serious ADRs collected according to section 11.3 should be signed off by investigator separately.

The completed CRFs are the sole property of the sponsor and should not be made available in any form to third parties, except for authorized representatives of appropriate governmental health or regulatory authorities, without written permission of the sponsor.

The study database will be set up and maintained by responsible CRO.

Paper Case report Form (pCRF)

Part of the study data will be collected using paper Case Report Form (pCRF). In the beginning of the study every site should select type of CRF. Whenever possible, complete data sets should be entered. Text field entries and any data collected on paper should be legible and follow the requested language standard.

All paper CRFs must be filled out legibly in black or blue ballpoint ink (use of black ink is preferred)/ Data are transcribed directly onto eCRFs.

Corrections to paper CRFs are to be made by making a single-line strikeout of the incorrect information and writing in the revisions. All corrections must be initiated and dated. Reasons for significant corrections should additionally be included. All new additions are to be made with the date and signature or seal affixed.

After the CRFs are transmitted to the sponsor/responsible CRO, any change of, modification of or addition to the data on the pCRF should be made by the investigator with use of change and modification records of pCRF (Data Clarification Form) provided by the sponsor/responsible CRO. Any changes to the data must be signed by the investigator.

Electronic Case Report Form (eCRF)

The sponsor or responsible CRO will supply investigators with access to eCRF. Patient data will be entered directly into the database by authorized investigators. The sponsor will make arrangements to train investigators in the use of the eCRF.

12.3.4. Coding of AEs and concomitant medications

Adverse events, medical history and concurrent medical conditions are coded with MedDRA dictionary (Medical Dictionary for Regulatory Activities). Concomitant Medication is coded with WHO Drug Dictionary.

12.3.5. Record retention

The investigator agrees to keep the records stipulated in Section 12.3.3 and those documents that include (but are not limited to) the study-specific documents, the Patient Identification list, medical records, all original signed and dated informed consent forms to enable evaluations or audits from regulatory authorities, the sponsor or responsible CRO. The study records should be retained until an amount of time specified by applicable regulatory requirements or for a time specified in the Study agreement. The investigator should contact and receive written approval from the sponsor before disposing of any such documents.

13 Statistical Methods and Determination of Sample Size

A statistical analysis plan (SAP) will be prepared and finalized prior to database lock. This section describes the statistical analyses as foreseen at the time of planning the study. Any known deviations from the planned analyses, the reason for such deviations and all alternative / additional statistical analyses that may be performed as well as the final statistical analysis must be described in a revised Statistical Analysis Plan (SAP) before completion of data collection. All later deviations and / or alterations will be summarised in the Clinical Study Report.

13.1 Patient Population

Due to observational nature of this study patients will not be excluded from analysis based on their performance and/or data availability. All obtained data will be summarised after procedures of data cleaning and verification. All planned analyses (including descriptive analyses and study listings) will be performed for Full Analysis Set of data.

The following patient's populations will be included into statistical analysis:

- *Safety population*: Patients who have taken at least one dose of Edarbi® after enrolling in the study (Baseline visit)
- *All Patients Enrolled population*.

13.2 The study data and Statistical Analysis methods

This study is observational and epidemiological methods will be employed for data analyses. Descriptive analysis will be performed of all collected data except data collected only for the purpose of data cleaning, i.e. all data listed in section 9.

The primary and secondary outcomes of the study are presented in section 6.2.

13.2.1. Summary of study data

All continuous variables will be summarised using the following descriptive statistics: n (non-missing sample size), mean, standard deviation, median, 25 percentile, 75 percentile, maximum and minimum. The frequency and percentages (based on the non-missing sample size) of observed levels will be reported for all categorical measures. For variables marked “binary” exact (Clopper-Pearson) 95% confidence intervals will be calculated where appropriate. For categorical variables with more than 2 categories 95% confidence intervals will be calculated using Goodman’s method [8].

In general, all data will be listed, sorted by site and patient, and when appropriate by visit number within patient. All summary tables will be structured with a column for each cohort in the increasing order and will be annotated with the total population size relevant to that table/dose cohort, including any missing observations.

The baseline visit is defined as the last observations collected prior to administration of the study drug.

Patient Disposition

Data regarding how many patients reached the various stages of the trial, how many dropped out, discontinued the treatment and for what reasons (death, ADRs, treatment failure, withdrew consent, lost to follow-up) will be presented for each subgroup and for study in bulk. Standard CONSORT diagram describing study patient flow will be provided

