4.2 Definition of Terms

According to guidelines of the Russian Ministry of Health for the management of HTN, [6] protocols of the Republic of Kazakhstan on clinical diagnosis and treatment of hypertension and protocol on the management of patients with type II diabetes [7,9]:

Target Blood Pressure (BP) –, target BP for all categories of patients is <140/90 mm Hg, except of patients with diabetes in whom target BP is <140/85 mm Hg.

Target Distolic Blood Pressure (DBP) –, target DBP for all categories of patients is <90 mm Hg, expect of patients with diabetes in whom target BP is <85 mm Hg

Target Systolic Blood Pressure (SBP) –, target SBP for all categories of patients is <140mm Hg

BP response – decrease of SBP \geq 20 mm Hg or decrease of DBP \geq 10 mm Hg

Overweight – elevation of body mass index (BMI) is from 25 to 30

Obesity – elevation of BMI > 30 [8, 9]. Obesity is divided for 3 classes according to severity.

Class of obesity	BMI
Obesity class 1	30-34,9
Obesity class 2	35-39,9
Obesity class 3	BMI \geq 40

Metabolic syndrome – according to the definition of the Russian Ministry of Health for the management of HTN [6], metabolic syndrome is diagnosed in the presence of main criterion and 2 any additional criteria listed below:

Main Criterion	Men	Women
waist circumference	\geq 94 cm	\geq 80 cm
Additional Criteria	Men	Women
low-density lipoprotein cholesterol	>3.0 mmol/l	>3.0 mmol/l
high-density lipoprotein cholesterol	<1.0 mmol/L	<1.2 mmol/L
triglycerides	>1.7 mmol/L	>1.7 mmol/L
impaired glucose tolerance	post-load plasma glucose 7.8	post-load plasma glucose 7.8

(post-load plasma glucose)	- 11.0 mmol/L	- 11.0 mmol/L
fasting glucose	6.1 - 7.0 mmol/l	6.1 - 7.0 mmol/l

5 Introduction

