9.4.5 Discontinuation/withdrawal of patients from the study

9.4.5.1. Criteria for Discontinuation or Withdrawal of a patient

Patients may be discontinued from study or study drug at any time, at the discretion of the investigator. Specific reasons for discontinuing a patient from the study are:

1. Voluntary withdrawal of informed consent in patient's request or at the request of patient's legally acceptable representative.

The patient (or patient's legally acceptable representative) wishes to withdraw from the study. The reason for withdrawal, if provided, should be recorded in the CRF. Note: All attempts should be made to determine the underlying reason for the withdrawal and, where possible, the primary underlying reason should be recorded (ie, withdrawal due to an AE or lack of efficacy should not be recorded in the "voluntary withdrawal" category).

2. Development of exclusion criteria or other safety reasons (not a AE or SAE) during the study.
3. Adverse Events (AE)/ Serious Adverse Events (SAE), including Patient's death

The patient has experienced an AE or SAE that requires early termination because patient is unwilling to continue because of the AE or SAE or continuation of patients' visit to the clinic is impossible or any other occurrence which can be happened.

4. Protocol deviations, incorrect enrolment of the patient. The investigator and the sponsor will decide whether there is a deviation from the protocol.
5. Lost for observation within the framework of the study. The patient did not return to the clinic and attempts to contact the patient were unsuccessful.
6. Study termination. Sponsor decision or regulatory authorities' requirement about cessation of the study.
7. Pregnancy. The patient is found to be pregnant.

Note: If the patient is found to be pregnant, the patient must be withdrawn immediately.

8. Other (specify)

If the patient is lost for observation within the framework of the study that is, it is impossible to conduct the final visit; the investigator must do its best to get in touch with the patients for getting full information and clarifying the reasons of the loss of contact. Premature end of HTN treatment by Edarbi® automatically means end of data collection.

Details for the premature termination of the study/sites as a whole are provided in section 9.6 (Premature termination or Suspension of Study or Investigational Site).

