13.2.4. Potential study biases

The study limitations are those inherent to uncontrolled observational studies. Taking into account observational and uncontrolled nature of the study, fully evaluating of azilsartan medoxomil efficacy will not be available. However data regarding blood pressure (SBP and DBP) dynamic during and after azilsartan medoxomil titration in real-life practice will be gathered and analyzed. The inclusion criteria are those that used when administering azilsartan medoxomil in practice and therefore, the same criteria as those that would have been used if we had performed a similar prospective study. This type of experimental design should prevent selection bias that could occur when patient enrollment is related to the development of the outcome. In prospective observational study like this attrition bias is possible, however, in case of early leaving study last BP data will be gathered and efficacy will be estimated, these cases will not be excluded from efficacy analysis.

Details of the statistical analyses will be presented in the Statistical Analysis Plan.

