13.2.5. Data handling

13.2.5.1. Missing data and invalid data

Missing data will not be restored. No procedures for missing data pattern assessment and/or imputation are planned. Outlier detection will be performed during blind data review, using modified Z-score([32] calculation

$$M_i = \frac{0.6745(x_i - \tilde{x})}{\text{MAD}},$$

with MAD denoting the median absolute deviation and \tilde{x} denoting the median.

Values of modified Z-score >3.5 will be considered outliers for univariate data sets that are assumed to follow an approximately normal distribution. If the normality assumption for the data being tested is not valid, then a determination of outlier using interquartile range and median (values more than 1.5 times the interquartile range will be considered outliers). Outliers will not be excluded from primary analysis *en bloc*, however, the medical context for each outlier will be defined and appropriate action taken. List of outliers flagged and actions taken will be included into Statistical Analysis Report. An additional sensitivity analysis will be performed excluding outliers.

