5. STATISTICAL / ANALYTICAL ISSUES

Visit windows

In accordance with the protocol, due to the non-interventional study design it's not possible to appoint exact times for the study visits, although it is expected that the period of observation will be approximately 6 months. The frequency of the visits will be assigned by each physician according to their routine practice. It is anticipated that the patients will visit their physician every 3 months and more often at the beginning until the patient achieves target blood pressure.

So, for the analysis and summary of clinical laboratory, efficacy, and safety data in case of this analysis/summary performed on "by visit" base. In the event of multiple values for an assessment within an analysis window, the value closest to the scheduled visit date will be used for analyses. If two values tie as closest to the time point (for example, one value is before and the other value is after the time point), then the later value will be selected as the analysis value.

Analysis Window	Start	End	Target Asses dupli	sment to be used if cates	
Baseline visi	t <1		NA		
Month 1 Month 3 Month 6	2 46 136	45 135 NA	30 90 Closes 180 equidi	st to target day, if stant use later result.	

The definition for the study days included in each study window is defined as below:

Treatment Day prior to first dose = Visit Date – Date of First Dose

Treatment Day on or after first dose = Visit Date – Date of First Dose + 1

Adjustments for Covariates

No specific adjustments for covariates will be made in all statistical analyses, unless specified otherwise per-analysis level.

Handling of Dropouts or Missing Data

Missing efficacy outcomes will be assumed to be missing at random (MAR) and thus will not be imputed in the primary analysis. However, if greater than 1% of all primary/secondary outcomes that should be available for analysis are missing, a sensitivity analysis will be undertaken in addition to the primary MAR analysis.

Confidential

This sensitivity analysis will include an evaluation of the results of models developed under the assumptions of:

1) last observation carried forward;

2) worst extreme case imputation and;

3) regression model imputation using all available information.

Outlier identification

During data Quality Control outlier identification will be performed using adjusted Z-score method (Iglewicz and Hoaglin, 1993).

$$M_i = \frac{0.6745(x_i - \tilde{x})}{MAD}$$

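### Visit 4 response and target-BP percentages count only non-missing patients, so early stoppers normally drop out of them, in conflict with Protocol 13.2.4

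*Protocol*

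**What the plan says.** The binary secondary outcomes are BP response and target BP at Visit 4, with target BP also reported by subgroup. Both are defined by BP values alone (Protocol 4.2, SAP 3).

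- **Denominator.** Protocol 13.2.1 and SAP 3 give the same rule: "The frequency and percentages (based on the non-missing sample size) of observed levels will be reported for all categorical measures".
- **After stopping.** Protocol 9.4.5.1: "Premature end of HTN treatment by Edarbi® automatically means end of data collection".
- **Missing data, protocol.** Section 13.2.5.1: "No procedures for missing data pattern assessment and/or imputation are planned".
- **Missing data, SAP.** Section 5: "Missing efficacy outcomes will be assumed to be missing at random (MAR) and thus will not be imputed in the primary analysis". It adds that "if greater than 1% of all primary/secondary outcomes that should be available for analysis are missing, a sensitivity analysis will be undertaken", using last observation carried forward, worst-case and regression imputation. This SAP covers the Kazakhstan data only (SAP 4).
- **Visit windows.** In SAP 5 the Month 3 window is Days 46 to 135 and the Month 6 window opens at Day 136. SAP 10 moves early-withdrawal visits to the closest scheduled visit, but only for safety variables.
- **Text pointing the other way.** Protocol 13.2.4 expects the last BP of early leavers to be gathered and says "these cases will not be excluded from efficacy analysis". Protocol 9.4.5.2 brings withdrawn patients' data into the final analysis. Protocol 13.1 says "patients will not be excluded from analysis based on their performance and/or data availability".

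**The concern.** The secondary objectives ask what proportion of overweight or obese patients respond to Edarbi or reach target BP. A patient who stops in the second month, because BP is not controlled or because of an adverse event, normally has no Visit 4 value. Under the non-missing rule that patient is absent from both numerator and denominator. The reported percentage becomes the success rate among patients still on treatment and still observed at about six months, which is a narrower question than the objective asks.

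Section 13.2.4 promises something different. It does not say how a last BP taken early becomes a Visit 4 value, so two analysts following different sections could report different rates from the same data. The plan allows for 25% dropout, so the choice could matter.

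**Working it through.** **1. The plan's own figures.** Protocol 13.4 gives SD 17.79, correlation 0.4375, 95% CI half-width 1 mm Hg and probability 0.9 (conditional). The SD of the paired difference is 17.79 × √(2 × (1 − 0.4375)) = 18.869. The exact conditional calculation gives 1437 pairs with probability 0.903, as stated. With 25% dropout, 1437 / 0.75 = 1916, as stated. Planned dropouts are 1916 − 1437 = 479.

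**2. What happens to a patient who stops at Day 60.** Data collection ends (Protocol 9.4.5.1). A BP taken at the stop falls in the SAP's Month 3 window. No efficacy rule moves it to Month 6, and nothing is imputed in the main analysis. The Month 6 value is missing and the patient leaves that percentage. If 13.2.4 is followed and the last BP is used instead, the patient stays in and is classified by that BP. On that reading, someone who stopped for an adverse event with BP at target counts as a success.

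**3. Size.** The documents give no expected response or target rate, so 60% among 1437 is an assumption: 0.60 × 1437 = 862 successes, exact 95% CI 57.4% to 62.5%. They also give no split of dropout by reason, so the share of the 479 who stop for lack of effect or an adverse event is varied. These patients enter the denominator as failures, and the remaining dropouts are left out:

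| Share of 479 | Added failures | Rate |
|---|---|---|
| 10% | 48 | 862 / 1485 = 58.0% |
| 25% | 120 | 862 / 1557 = 55.4% |
| 50% | 240 | 862 / 1677 = 51.4% |

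The lower bound counts every dropout as a failure: 862 / 1916 = 45.0% (exact 95% CI 42.7% to 47.2%). It takes all 1916 enrolled patients as having had at least one dose.

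**4. Direction.** If missing patients would succeed at rate q, the all-patient rate is 0.75 × 60% + 0.25 × q:

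| q | 0% | 20% | 40% | 60% | 80% |
|---|---|---|---|---|---|
| All-patient rate | 45% | 50% | 55% | 60% | 65% |

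The non-missing figure is too favourable only when q is below 60%, or when a stop is itself defined as a failure.

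**The case against.** The strongest reply is that the plan does not settle on losing these patients. Protocol 13.2.4 keeps them in the efficacy analysis. At premature end of Edarbi, Protocol 10.5 also requires the last appropriate visit form, and visit data include BP (10.4). This stands: the documents conflict, and a reader who infers that the rates are certainly inflated goes beyond them. But 10.5 does not make that form a Visit 4 form, and no efficacy rule places the value there.

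Second, response and target BP are BP-only definitions, so treating a stop as a failure creates a composite outcome that the plan does not state. This also stands. It is a choice about what the rate should mean, and must be labelled as one.

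Third, much of the transparency is already planned. Tables carry the total population including missing observations, disposition is given by reason and subgroup (Protocol 13.2.1, SAP 6), and reasons for stopping Edarbi are tabulated (SAP 9.2). With 25% planned dropout, the SAP's 1% trigger for sensitivity analyses would very probably be met. These measures help a reader to see the gap, but the percentages and their intervals still rest on non-missing patients. The sensitivity analyses are secondary, do not say how worst case applies to a binary outcome, and sit in a Kazakhstan-only SAP. The whole-study SAP was not supplied, so its handling is unknown.

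Fourth, Protocol 13.1 can be read as a rule about analysis populations, since a patient without Visit 4 still contributes at Visits 2 and 3. That is fair; the clear conflict is with 13.2.4.

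**Conclusion.** The concern holds in a limited form. As written, the percentage rule normally yields Visit 4 rates for patients still on Edarbi, and it conflicts with 13.2.4. Those rates are likely, not certain, to be too favourable.

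At an assumed 60% observed, stops for lack of effect or an adverse event lower the rate by about 2 to 9 points when they make up 10% to 50% of planned dropouts. The smallest of these shifts lies inside the sampling interval of 57.4% to 62.5%; the other two do not. The 15-point gap to 45.0% is a bound, not an estimate, because the 25% is a general allowance that may include losses unrelated to effect or tolerability.

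Two further inferences are tempting but unsupported. One is that subgroup rates would be misordered: the documents give no stopping rates by subgroup. The other is that the study rates would be overstated against the control rates of 22% and 15% in Protocol 5.3: those are background on unmet need, and no comparison with them is planned.

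This affects secondary outcomes only. It is a worthwhile, inexpensive improvement and does not undermine the primary analysis.

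**What to change.** 1. Reconcile Protocol 9.4.5.1, 13.2.1, 13.2.4 and 13.2.5.1 with SAP 3 and 5, and state one denominator rule for the Visit 4 response and target-BP proportions. Say whether, and how, a last BP taken before the Month 6 window is used.
2. Report these proportions, overall and by subgroup, over all Full Analysis Set patients (defined in SAP 9; named but not defined in Protocol 13.1). Count stops for lack of effect or an adverse event as not achieving. Count other missing patients as not achieving too, labelled as a conservative bound. This avoids a lopsided denominator that keeps known failures and omits the other missing patients.
3. Print the non-missing percentage beside it, with the number missing by reason.
4. State plainly that counting a stop as not achieving is a composite definition added to the BP-only one.

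The End of Observation form already records the reason for stopping and the last intake date (Protocol 10.5), so no new data are needed and patient care is unaffected. The cost is SAP wording, one extra derivation and less favourable reported rates.
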